Brief Summary	This is a single-arm, open-label feasibility study. A maximum of 30 participants will be enrolled. 15 participants will be assigned and will undergo a novel neurofeedback intervention, targeting down-regulation of deep limbic structures, specifically the amygdalae. Participants will complete 15 neurofeedback sessions delivered twice weekly over 8 consecutive weeks. The intervention will be delivered via the PRISM platform.	
Phase	Pilot	
Objectives	1)Train the NYU team on the electric finger print electroencephalography neurofeedback (EFP-EEG-NF) technology and provide them with hands-on experience; 2) Assess participants' ability to learn the feedback paradigm (i.e. control the EFP-EEG-NF signal; time to achieve learning; assess learning curves); 3) Explore preliminary results assessing emotional dysregulation measured on subsets of AISRS and BRIEF-A.	
Methodology	Open label	
Endpoint	Primary: Demonstrate the NYU team can successfully recruit, enroll, and complete the protocol as proof of concept and collect high-quality analyzable data; Secondary: Clinically meaningful improvement on primary outcome measures (AISRS and BRIEF-A) demonstrated by effect size of change.	
Study Duration	1 year	
Participant Duration	11 weeks	
Duration of IP administration	8 weeks	

Population	Adults ages 18-60 with a diagnosis of Attention Deficit/ and Hyperactivity Disorder-Adults (ADHD) who otherwise meet study inclusion and exclusion criteria.
Study Sites	New York University School of Medicine
Number of participants	30 participants expected to be enrolled; 15 expected to complete the study
Description of Study Agent/Procedure	Neurofeedback sessions will be delivered via the PRISM system. This is a non-significant risk device.
Reference Therapy	N/A
Key Procedures	Clinical evaluation, EFP-EEG-NF training, EFP-EEG-NF sessions, AE evaluation, and participant satisfaction measures.
Statistical Analysis	This is a pilot study and is not formally powered to assess effect statistically. See Statistical Explanation section

Page 9

1 Key Roles

[name], Principal -Investigator

Department of Psychiatry NYU Grossman School of Medicine [name] [contact] [contact]

[name], Co-Investigator Department of Psychiatry NYU Grossman School of Medicine [name] [contact] [contact]

[name] Department of Psychiatry NYU Grossman School of Medicine [name] [contact] [contact]

2.1 Background Information and Relevant Literature

Attention-deficit/hyperactivity disorder (ADHD) is a neuropsychiatric disorder characterized by problems with sustaining attention, organization, planning, procrastination, day-dreaming, restlessness, impulsivity and hyperactivity. ADHD is most frequently associated with being a disorder impacting children and adolescents, however, its prevalence in the adult population is becoming increasingly more acknowledged. A replication of the National Comorbidity Study estimated approximately 4.4% of the U.S. population aged 18-44 years to meet criteria for adult ADHD (Kessler RC et al. 2006). Recent factor analyses ([name] et al. 2017) have underlined the importance of co-travelling symptoms of executive function deficits, such as difficulty with organization, planning, time management and working memory, in addition to the core symptoms of inattention and hyperactivity-impulsivity addressed in the Diagnostic and Statistical Manual of Mental Disorders, 5th edition (DSM-5) (American Psychiatric Association 2013). According to Barkley and Murphy (2010), executive function deficits define the impairment in ADHD. Executive function deficits can cause impaired attention, impulsive decision making, irritability, and other common symptoms of ADHD (Barkley and Murphy 2010).

Pharmacotherapy is one of the most common forms of treatment for ADHD. Stimulant medications, such as amphetamine (i.e. Adderall- mixed amphetamine salts, Dexedrine-dextroamphetamine) or methylphenidate (i.e. Concerta, Ritalin, Focalin) formulations, have been shown to be highly efficacious treatments for child and adolescent ADHD (Newcorn et al., 2017) and for adult ADHD (amphetamine: Weisler et al., 2017; Spencer et al., 2008; methylphenidate: Bron et al., 2014; [name] et al., 2009).

CONFIDENTIAL

Page 12

Stimulant medications come in various dosages: long-acting doses, such as extended-release, that can last all day and shortacting doses, such as immediate-release, that only last a couple hours and can require multiple doses throughout the day. The most common side-effects reported with taking a stimulant are appetite suppression and sleep disruption, more particularly ability to fall asleep (Biederman et al., 2004). Non-stimulant medications are another efficacious treatment option for adults with ADHD. Medications such as atomoxetine (i.e. Strattera) and antidepressants (i.e. Wellbutrin) are commonly used non-stimulants to treat ADHD. Atomoxetine has been shown to be a clinically effective treatment option for ADHD. However, when compared to a stimulant, such as methylphenidate, it has been found that stimulant medications are more effective than non-stimulants (Liu et al., 2017; Newcorn et al., 2017). While pharmacological treatments of ADHD have shown to be very efficacious, they are not preferred by all due to the side effects and draw of psychological treatments. Thus, there is a need to explore alternative and adjunctive therapies to improve outcomes for those with ADHD.

Functional Magnetic Resonance Imaging (fMRI) studies conducted in subjects with ADHD suggest that, compared to healthy controls, those with ADHD may suffer from deficits in brain regions involved in emotion regulation and executive control (Hwang et al., 2015; Shaw et al., 2014). These areas include the amygdala (Maier et al., 2014; Brotman et al., 2010), a central area of the limbic system known as the "emotional brain," and the prefrontal cortex (Passarotti et al., 2010). To date, most findings indicate that, compared to healthy controls, ADHD subjects have increased activity in the amygdala in response to subjective unpleasant or fearful stimuli, and no amygdala activity when shown pleasant stimuli (Tajima-Pozo et al., 2018; Brotman et al., 2010). Furthermore, some studies have shown increased activity in frontal lobe regions associated with emotion processing, regulation and valence; most notably in the medial prefrontal cortex (mPFC) (Posner et al., 2011). Additional studies have found significant negative genetic correlations between ADHD, intracranial volume (ICV) and areas such as the amygdala (Klein et al. 2019).

Such hyperactivity in certain brain regions when viewing unpleasant or fearful stimuli suggests deficits in emotion regulation, which indicates the potential for reversing the pathological process that occurs in ADHD. That is, a relevant mental intervention that involves these areas and pathways may create a process that is opposite in direction relative to the pathology, and which may alleviate and improve the symptoms of ADHD. One of the common tools used for such therapeutic mental intervention is bio-feedback. The source of feedback can be related to blood pressure, pulse, cutaneous conductivity and more. It can also be based on brain activity as measured by EEG or by brain MRI scans; this method is called neurofeedback (NF).

During NF training, subjects are asked to change brain area activity based on feedback derived from signals coming from their own brain, which is mediated by some (visual or auditory) stimulus. The subject is asked to find the mental strategy to influence the characteristics of the stimulus, such as lowering the volume of music played to their ears or changing something visually in a visual interface. A change in stimulus properties is a recurrence of the change in activity in the target area of the brain (Myers & Young, 2012). There is a growing body of studies in the published literature, in which electrical brain activity (assessed using the EEG) served as the source for neurofeedback, as reviewed in:(Van Doren et al., 2019). These studies have shown that, in the context of feedback, humans are able to alter their brain activity and improve cognitive and behavioral control. Moreover, evidence supporting EEG-NF has accumulated as a therapeutic tool for ADHD (meta-analysis by Arns et al., 2020). However,

CONFIDENTIAL

some studies have found conflicting evidence that does not support EEG-NF as an effective treatment for ADHD (Schonenberg et al., 2017; Cortese et al., 2016).

The significant drawback of existing EEG-NF methods lies in the fact that the EEG device has low spatial resolution, and therefore does not allow the detection of activity originating in deep brain regions, emotional regions known to be associated with ADHD development such as the amygdala, hippocampus and mPFC. In recent years, real-time fMRI (rt-fMRI) has been used to train subjects to regulate deep-area activity (reviewed in (Chiba et al., 2019; Linhartová et al., 2019; Young, 2019)). Multiple studies also show that subjects can be trained to regulate the activity of a network that includes mPFC and limbic areas, and thus can possibly have an effect on ADHD markers such as deficits in inhibition and decision making (Baumeister et al., 2018; Hauser et al., 2014; Vernon et al., 2004). Furthermore, it is also found that by providing fMRI, subjects can be trained to regulate the activities of networks that have been found to be associated with reward processing, an ability that is critical for managing symptoms of ADHD (Baumeister et al., 2019). The disadvantage of this method is that the fMRI test is expensive and cumbersome to the subject, and the MRI device through which it is performed is not portable and its accessibility is low. Relative to fMRI, Electroencephalogram (EEG) constitutes a much more scalable recording device, however, it suffers from the aforementioned drawbacks.

[name] team implemented the amyg-EFP in a neurofeedback (NF) paradigm (termed the amyg-EFP-NF) and demonstrated, through randomized controlled studies, that: healthy individuals can learn to down-regulate the EFP signal (Keynan et al., 2016; Meir-Hasson et al., 2016), and that this translates into down-regulation of the amygdala blood oxygen level– dependent activity (BOLD) activity, as measured by real-time fMRI(Keynan et al., 2016, 2019). This was the first ever EEG-NF intervention that enabled precise, targeted self-modulation of a sub-cortical region. Furthermore, results from these studies demonstrated that participants who were trained outside the fMRI-scanner to down-regulate their amygdala EFP index not only successfully decreased amygdala BOLD activity during fMRI-NF in a following session, but also showed reduced amygdala reactivity to threatening visual stimuli (Keynan et al., 2016). In addition, amyg-EFP-NF led to improve emotion regulation as demonstrated behaviorally by a well-stablished emotional conflict task, and in the neural aspect by enhanced amygdala-vmPFC functional connectivity (Keynan et al., 2019).

2.2 Name and Description of the Investigational Agent

The device to be used in this study (called PRISM) constitutes a non-significant risk device (see rationale below). It is an investigational software under development, intended to be used in research studies testing the clinical efficacy of an innovative paradigm for EEG-based neurofeedback.

Off-the-shelf research-grade EEG hardware (Nautilus: Nautilus Research Wearable EEG Headset, wireless 16 electrode cap and amplifier system) will be used in conjunction with the PRISM software.

The EEG-based neurofeedback device (PRISM) to be used in this study is/does NOT:

CONFIDENTIAL

- Intended as an implant and presents a potential for serious risk to the health, safety, or welfare of a subject.
- Purported or represented to be for use supporting or sustaining human life and presents a potential for serious risk to the health, safety, or welfare of a subject.
- For a use of substantial importance in diagnosing, curing, mitigating, or treating disease, or otherwise preventing impairment of human health and presents a potential for serious risk to the health, safety, or welfare of a subject.
- Otherwise presents a potential for serious risk to the health, safety, or welfare of a subject.

2.2.1 Clinical Data to Date

Earlier studies have pointed to hyper-activation of the amygdala as an indication of lower emotional processing and less control of impulsivity in those with ADHD (Tajima-Pozo et al., 2018; Brotman et al., 2010), and suggested that down-regulating or reversing its activity may address emotional reactivity and regulation deficits common in ADHD patients (Schulz et al., 2014).

The amyg-EFP-NF method was thus applied in a randomized controlled study (NCT02020265) involving a large cohort of healthy military cadets undergoing stressful boot camp training (Keynan et al., 2019). Results indicated that repeated amygdala-EFP training sessions, as compared to a common form of EEG-neurofeedback, based on the alpha/theta ratio, had a beneficial effect on neural and behavioral indices of stress resilience, pointing at EFP-NF as a plausible, scalable, non-pharmacological yet neuroscience-based training method to prevent stress-induced psychopathology.

Amyg-EFP-NF was further tested in a randomized controlled trial (NCT02544971) aimed at down-regulating amygdala activity in PTSD patients. Results showed that patients learned to volitionally down-regulate their Amyg-EFP signal and demonstrated reduction in PTSD symptoms, compared to the No-NF (control) arm (Fruchtman-Steinbok et al., 2019). Here too, superior down-regulation of amygdala BOLD signal during fMRI-NF following the intervention in the treatment arm, compared to controls, confirmed target engagement. These results establish the Amyg-EFP as a plausible, mechanism-driven, intervention for PTSD.

Finally, in a separate line of research, EFP-NF was administered to patients suffering from Fibromyalgia, a chronic pain syndrome that involves, among other symptoms, sleep disturbance and emotion dysregulation (Goldway et al., 2019). These symptoms are known to be mediated by heightened limbic activity and so it was speculated that Amyg-EFP-neurofeedback training aimed at limbic down modulation (relative to sham-training) would improve the clinical status of Fibromyalgia patients. Results indeed revealed an improvement in objective sleep measures as well as delayed improvement in chronic pain and subjective sleep experience, indicating that EFP-NF may serve as a novel approach to treat Fibromyalgia.

Altogether, these studies conducted by the [name] lab demonstrate GrayMatter Health's ability to develop and utilize a scalable EEG-NF probe in order to precisely modulate deep mesolimbic sub-cortical regions, such as the amygdala. Importantly, the effects of the NF training via the EFP were not restricted to neural indices, but also facilitated real-life psychological changes in

regulating stress, suggesting its potential in modifying other regulatory mechanisms, such as emotion regulation. To date, there have been no studies testing Amyg-EFP-NF on patients, more specifically adults, with ADHD. This pilot study serves to set the course for the analyzing how this tool can help regulate symptoms or behaviors common in ADHD patients.

2.3 Rationale

Approximately 4.4% of the U.S. population aged 18-44 years meet criteria for adult ADHD based on a replication of the National Comorbidity Study (Kessler RC et al., 2006). ADHD is a neuropsychiatric disorder characterized by problems with sustaining attention, organization, planning, procrastination, day-dreaming, restlessness, impulsivity and hyperactivity. Psychostimulant medications are the mainstay for treating ADHD as they have shown to be highly effective in symptom reduction. Non stimulant medication is highly recommended as a first-line of treatment for ADHD as well for those who cannot tolerate the side effects some stimulant medications may carry. Psychological treatments have been found to be moderately effective for treating ADHD. Compared to pharmacotherapy, the effect sizes are smaller but the promise for treating ADHD with nonpharmacological interventions is there (Cortese et al., 2015; Sonuga-Barke et al., 2013). Cognitive Behavioral Therapy (CBT) has been shown to be efficacious in improving symptoms of ADHD in various clinical and randomized controlled trials. Especially when combined with a pharmacotherapy, CBT has shown positive results in controlling symptoms of ADHD (Ramsay & Rostain 2014). However, the evidence basis for psychosocial therapies as a stand-alone treatment for ADHD still require more research. Thus, there is a clear need to expand upon the nonpharmacological evidence base and explore alternative and adjunctive therapies to improve outcomes for patients with ADHD. This pilot study will demonstrate that the NYU team can successfully recruit, enroll, and complete the protocol as proof of concept and collect high-quality analyzable data in preparation for later clinical trials.

2.4 Potential Risks & Benefits

2.4.1 Known Potential Risks

Risk of Breach of Confidentiality: Participation in research involves potential loss of confidentiality or privacy. To mitigate this risk, research records will be kept as confidential as possible through use of a coding system with linkage restricted to IRB-approved NYU study personnel. All data will be stored confidentially, as described in sections 11 and 13.5.

Risk of Assessment Procedures: There are no known psychological risks associated with the clinical interview or questionnaires used in this study and all have been used extensively in clinical populations. It is possible that discussion about psychiatric symptoms may cause emotional discomfort or temporary distress in some participants. To mitigate this risk, the consent form will fully inform participants about the nature of the information to be disclosed and that they may refuse to answer individual questions or withdraw from the study in its entirety at any time. Qualified research staff is available to provide support to participants who experience emotional distress. Elevated distress (e.g. anxiety) is not expected to persist beyond the timeframe of the assessment.

Risk of Neurofeedback Procedures:

The EEG test is a tool that is routinely used in medicine for recording brainwaves. The received signals are based on the electrical activity of the brain. There is no known risk in EEG recording; however the EEG electrodes may cause slight discomfort. If there is a great deal of discomfort, the examination will be terminated at the request of the participant. EEG electrode contact with the scalp is augmented using special gel that is applied to the scalp. This gel can easily be removed by washing the hair after the neurofeedback session.

2.4.2 Known Potential Benefits

Participants may or may not experience clinical benefit from this study. Aspects of study participant likely to provide direct benefit to participants include close psychiatric monitoring.

3 Objectives and Purpose

3.1 Primary Objectives

The primary objectives of this pilot study are as follows:

- 1. To train the NYU team on EFP-EEG-NF technology and provide them with hands-on experience.
- 2. To assess participants' ability to learn the feedback paradigm (i.e. control the EFP-EEG-NF signal; time to achieve learning; and assess learning curves).
- 3. To explore preliminary results assessing emotional dysregulation measured on subsets of AISRS and BRIEF-A.

4 Study Design and Endpoints

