4.2 Study Endpoints

4.2.1 Primary Study Endpoints

Demonstrate the NYU team can successfully recruit, enroll, and complete the protocol as proof of concept and collect high-quality analyzable data.

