4.2.2 Secondary Study Endpoints

30% meaningful improvement on primary outcome measures (AISRS and ASRS/BRIEF-A) demonstrated by effect size of change scores.

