- 3. Neurocognitive Testing: Participants will complete a standardized, neuropsychiatric battery through WebNeuro, an abbreviated form of IntegNeuro. WebNeuro is a well-validated, HIPAA-compliant internet-delivered testing battery that probes a wide range of neurocognitive functions. The battery consists of performance-based tests previously validated for remote delivery. Domains include executive functions such as attention/working memory, focus/inhibition, task-shifting, emotion recognition, emotional biasing of attention, and emotion regulation. Data from WebNeuro is linked to the standardized and integrative Brain Resource International database and cognitive functioning domain outputs are computed via WebNeuro software algorithms.
- 4. EFP-EEG-NF training: Each NF training session consists of 5 consecutive sequences of NF presentations. Prior NF session initiated a global BL is performed (3 minutes). Following the global baseline a "watch" condition (60 seconds), in which participants are instructed to passively view the animation, and are told that the scenario is not influenced by their brain activity. In the "regulate" (3 minutes) participants are instructed to lower the room's unrest level. A "rest" phase (30 seconds) follows each sequence, allowing participants to relax.

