10.1 Statistical and Analytical Plans (SAP)

This pilot study is not formally powered to assess effect statistically. We will: demonstrate the NYU team can successfully recruit, enroll, and complete the protocol as proof of concept and collect high-quality analyzable data; and assess clinically meaningful improvement on primary outcome measures (AISRS and ASRS/BRIEF-A) as demonstrated by effect size of change.

As this is a pilot study and the full estimation of the potential magnitude of the effect is not known, we are planning an interim analysis after completion of approximately 10 patients with treatment data. This interim analysis examine the magnitude of clinical effects on clinical measures of AISRS expanded AISRS subsets (clinician symptom measure), ASRS (self-report symptom measure), BRIEF (self-report measure of executive function) and CGI (measure of impairment) via examination for means, SDs and magnitude of effect. Safety data will also be examined.

ADHD Rationale

In this study, approximately 30 subjects will be phone prescreened, which will give us at least 30 participants coming in for screening and consenting for participation. Up to 30 patients will be enrolled/consented to be sure that 15 evaluable/assigned

CONFIDENTIAL

patients reach the end of PRISM Intervention. We expect some of the subjects to screen fail either during the telephone phone screen or during the hybrid remote visit. Screen failures can occur during the MINI (psychiatric interview), ACDS (ADHD diagnosis interview) or upon discretion of the principal investigator. Subjects are also given the opportunity to continuously decide participation throughout the study. Subjects can opt out of the study at any time.

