13.5.1 Research Use of Stored Human Data

- Storage: Standard institutional practices will be followed to maintain the confidentiality and security of data collected in this study. Study staff will be trained with regard to these policies. Only IRB-approved NYULH study personnel will have access to identifiable data. Subjects will be assigned a code that will be used instead of their name, medical record number, or other personally identifying information. Electronic files for data analysis will only contain the subject code. The code will not contain any part of the 18 HIPAA identifiers. The key associating the codes with the subjects' personally identifying information will be restricted to the principal investigator and designated IRB-approved study staff. The key will be kept secure on a restricted NYULH network drive in a limited access folder. Electronic data will be stored on REDCap and will require NYULH ID/password authentication. All paper files containing restricted information will be secured in locked filing cabinets in restricted offices.
- Tracking: Data will be tracked using REDCAP. EEG-related data generated during the neurofeedback sessions will be produced, processed and stored on the local computer on which the PRISM software is installed. The data is stored as standard EEG data using EDF/BDF formats and includes both the raw EEG as well as the computed EFT values. The data will remain locally on the secure NYULH platform.
- PRISM Support: Gray Matters will provide technical support and service the PRISM software as needed during the study. To do so, Gray Matters personnel will connect remotely to the local computer on which the PRISM software is installed by connecting to the IP address of the computer. Remote support will entail accessing usage and error logs from the PRISM

CONFIDENTIAL

software as text files and HTTPS event logs. Gray Matters will remotely access anonymized participant EEG data generated by PRISM software. Error and events logs as well as anonymized EEG data will be uploaded to a secure and HIPAA-compliant cloud server, Amazon Web Service, AWS, to further develop and improve the PRISM software.

14 Data Handling and Record Keeping

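### Primary objective 2 (learning to control the EFP signal) has no endpoint and no planned analysis, and 15 is used both for participants assigned and for participants who complete

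*Combined protocol and SAP*

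**What the plan says.** **Learning.** The second primary objective in section 3.1 is to assess participants' "ability to learn the feedback paradigm (i.e. control the EFP-EEG-NF signal; time to achieve learning; and assess learning curves". The Objectives row of the Protocol Summary repeats it: "control the EFP-EEG-NF signal; time to achieve learning; assess learning curves".

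The only primary endpoint (4.2.1) is "Demonstrate the NYU team can successfully recruit, enroll, and complete the protocol as proof of concept and collect high-quality analyzable data". The secondary endpoint (4.2.2) is "30% meaningful improvement on primary outcome measures (AISRS and ASRS/BRIEF-A) demonstrated by effect size of change scores". Section 10.1 restates the feasibility aim and will "assess clinically meaningful improvement on primary outcome measures (AISRS and ASRS/BRIEF-A) as demonstrated by effect size of change". It adds an interim look, after about 10 patients, at AISRS, ASRS, BRIEF, CGI and safety.

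Section 7.1.1 describes sessions of five sequences with a watch "condition (60 seconds), in which participants are instructed to passively view the animation", and a three-minute regulate phase. Section 13.5.1 says the stored session data "includes both the raw EEG as well as the computed EFT values".

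**Numbers.** The Brief Summary states: "A maximum of 30 participants will be enrolled. 15 participants will be assigned and will undergo a novel neurofeedback intervention". The same table expects 15 to complete. Section 4.1 has 30 consented with enrollment capped at 15. Section 5.6 has about 30 enrolled to yield 15 evaluable. Section 10.1 treats enrolled and consented as one term (up to 30), and evaluable and assigned as one term (15, who are to reach the end of the intervention). Section 10.2 has about 30 consented for a goal of 15 completers. Section 5.7.2 rules out replacing withdrawals.

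**The concern.** Section 2.2.1 says this form of neurofeedback has not been studied in patients with ADHD. Whether these adults can learn to control the signal is therefore an open question, and the protocol makes it primary. Without an endpoint or an analysis, the report must either leave the question unanswered or use a definition of learning chosen after the signal data have been seen.

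The second issue is the feasibility result, which section 2.3 intends as preparation for later trials. If 15 is both the number who start and the number who must finish, one withdrawal means the goal is missed. The plan does not say whether that would count against the primary endpoint, because the goal in 10.2 and the endpoint in 4.2.1 are not linked.

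**Working it through.** **Step 1: follow objective 2 through the plan.**

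| Place | Feasibility | Clinical scales | EFP signal or learning |
|---|---|---|---|
| 3.1 and Protocol Summary, objective 2 | no | no | yes |
| 4.2.1 primary endpoint | yes | no | no |
| 4.2.2 secondary endpoint | no | yes | no |
| 10.1 main analysis | yes | yes | no |
| 10.1 interim analysis | no | yes, plus safety | no |

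Sections 4.2 and 10.1 are present and readable, so removed text does not explain the gap. The documents contain no learning index, no rule for when learning is achieved, and no model for the curve.

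The schedule in 7.2 gives two sessions in each of weeks 2 to 8 and one in week 9: 7 × 2 + 1 = 15 sessions. With 15 participants at full attendance, that is 15 × 15 = 225 session-level values with no planned use. I assume that the EFT values named in 13.5.1 are the EFP index.

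**Step 2: the plan's own sample-size figure.** Section 10.2 goes from about 30 consented to 15 completers. The documents give no screen-failure or dropout rate, so 30 cannot be derived. Working backwards, 15 / (1 − 0.50) = 30, an overall loss of 50% from consent to completion. Nothing says how that loss divides between screen failure and dropout after assignment.

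**Step 3: what the 15s imply together.** Suppose 15 start (the Brief Summary's assigned number and the 4.1 cap), nobody is replaced (5.7.2), and each participant drops out independently with probability d. Then:

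- P(all 15 complete) = (1 − d)^15
- Expected completers = 15 × (1 − d)
- Starters needed to expect 15 completers = 15 / (1 − d), rounded up

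The documents give no d, so a range is shown.

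| Assumed d | P(all 15 complete) | Expected completers | Starters to expect 15 |
|---|---|---|---|
| 5% | 0.95^15 = 0.463 | 14.25 | 16 |
| 10% | 0.90^15 = 0.206 | 13.5 | 17 |
| 20% | 0.80^15 = 0.035 | 12.0 | 19 |
| 30% | 0.70^15 = 0.005 | 10.5 | 22 |

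**Step 4: precision of a completion rate.** The exact (Clopper-Pearson) 95% interval is 78.2% to 100% for 15 of 15, and 51.9% to 95.7% for 12 of 15. Even a perfect result leaves a true completion rate just under 80% compatible with the data, so the denominator and the interval should both be reported.

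**Step 5: who is a completer?** The plan has several wordings: reaching the end of the intervention (10.1), completing 15 sessions (4.1), completing the protocol (4.2.1) and completing the study (Protocol Summary). By 5.5, participation runs to the post-intervention visit, which 7.2.5 places at Week 11. Someone who misses sessions but attends the last one, or who finishes the sessions but misses Week 11, is a completer on some of these readings and not on others.

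**The case against.** The best defense is that this is a small, open-label pilot, declared not formally powered, and that a descriptive study need not specify every analysis. That is fair as far as hypothesis tests go, and none is asked for. It does not excuse a stated primary objective with no measure at all.

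Four stronger readings are tempting, and the documents do not support them.

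- *That 30 may start the intervention, so 15 completers would be only 50% completion.* No section says this. Most of the 15-versus-30 conflict comes from using enrolled for both consent and treatment. Sections 5.6 and 10.1 leave open, but do not state, that more than 15 may start. Fifteen of 30 is completers over consented, not completion among starters.
- *That feasibility has no criterion whatever.* Fifteen completers is the plan's own goal, and the Protocol Summary gives a one-year duration. What is missing is the link to the endpoint in 4.2.1 and a meaning for high-quality analyzable data.
- *That a known share of non-learners would be called learners.* The documents contain no learning rule, so no such share can be computed. It would depend on the rule chosen and on the correlation between a person's sessions.
- *That attending the Week 9 session defines completion.* This is the loosest of several readings, and the plan does not choose it.

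It is also fair to say that no stated calculation is wrong. The defects are a missing specification and inconsistent terms.

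**Conclusion.** The learning gap stands firmly on the text: a primary objective has neither endpoint nor analysis, while data that could address it are to be stored.

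The inconsistency in numbers is real but narrower. On the sections that put 15 into the intervention, the goal of 15 completers is met only with zero dropout after assignment, with probability 46%, 21% or 3.5% at dropout of 5%, 10% or 20%. Those figures assume 15 starters, independent dropout and rates that the documents do not give. They would not apply if the sponsor clarifies that more than 15 may start. The completer goal also needs to be attached to the primary endpoint. Overall this is a cheap improvement that should be made.

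**What to change.** **1. Add EFP learning to 4.2 and 10.1.**

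- Measure: per-session mean EFP during regulate minus mean during watch, in everyone who starts session 1. First confirm that the stored files mark both phases; 13.5.1 does not say.
- Model: a linear mixed model over sessions 1 to 15 with random participant intercept and slope, allowing for within-person serial correlation and a non-linear session term.
- Report: mean change with 95% CI and the individual curves. With no control arm, this describes change over sessions and is not evidence of cause.
- Time to learning: fix one definition before any EFP data are examined, and state its false-positive rate under plausible session-to-session correlation.

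**2. Reconcile the numbers before setting a success rule.**

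- Make the Protocol Summary, 4.1, 5.6, 5.7.2, 10.1 and 10.2 agree on how many may be consented, how many may start and how many are expected to complete, using consented, started and completed as distinct terms.
- Restate the completer goal so that it is consistent with the starter limit and the no-replacement rule, and tie it to the endpoint in 4.2.1.
- Define completer once, choosing among the plan's own wordings (end of the intervention, 15 sessions, or the Week 11 visit), and report sessions attended.
- Report completers over starters and completers over consented, each with an exact 95% CI, and the share of attended sessions that yield an analyzable EFP value.

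**Cost.** Protocol and SAP wording plus modest extra analysis of stored data, with no new visits. The downside is that extra analysis and a feasibility claim that can fail.
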